2. Is this a multi-center study where the Penn IRB will be asked to serve as the IRB of Record for other external study sites?

No

Other Sites

No other sites

Protocol

Abstract

Cardiovascular disease is the leading cause of death in the US. While prevention approaches have improved longevity of patients, risk factors and adverse health behaviors (e.g., physical inactivity, smoking) are highly prevalent. The logistics and practicalities of meeting the goal of ideal CV health have not been clearly elucidated. Practice guidelines recommend using the Framingham risk score (FRS) or other risk prediction tools to classify patients risk of CV disease. These models however are imprecise and there is increasing focus on identifying markers that provide better measures of risk. As digital platforms are increasingly used to document lifestyle and health behaviors, data from digital sources may provide a window into manifestations of novel risk factors and potentially a better characterization of existing risk factors.

Objectives

Overall objectives

This study has three main objectives. (1) Identify and characterize topics and features derived from digital data (e.g., social media, online search, mobile media) which are associated with CHD and related risk factors and develop phenotypes of how patients use and engage with social media and then determine the association of these phenotypes with health status, social media perceptions, and patient activation. (2) Quantify and validate the incremental benefit of adding variables from patients' digital data to conventionally-derived predictive models of CHD (e.g. Framingham risk score/American College of Cardiology ASCVD Risk Estimator Plus) using a retrospective cohort of patients with and without heart disease. (3) In a cohort of patients with and without heart disease, develop and evaluate models that use digital media data to predict health care utilization (e.g. cost). (4) Evaluate the impact of dynamic health events (e.g. COVID-19) on modifiable CV health behaviors (smoking, diet, activity) using population level-digital media data (e.g. Facebook, Twitter)

Primary outcome variable(s)

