The primary outcome variable for the first objective will be topics and features (derived using the Latent Dirichlet Allocation [LDA] method for clustering language data) as well as a model-based approach of latent class analysis (LCA). We hypothesize: H1: There will be a difference in themes and topics posted by patients with heart disease and for patients without heart disease and use and engagement

phenotypes reflecting quantity, quality, and interaction of posts will be associated with health status, social media perceptions, and patient activation. The second objective outcome variable will be any CHD event. We hypothesize: H2: Adding digital data variables to conventionally-derived predictive models will improve the AUC for forecasting/predicting a CHD related event in a patient. The third objective outcome measure will be health care utilization measured by cost. We hypothesize: H3: Unique digital data variables identified for patients with heart disease and without heart disease will better predict future health care utilization costs for the health system. The fourth objective outcome measure will be the impact of dynamic health events on CV health behaviors. We have the following three hypotheses: H4,1: Digital media data will provide valid measures of health behaviors when compared with traditional sources. H4,2: Variations in digital data about modifiable CV health behaviors will correlate with dynamic health events. H4,3: Modifiable CV health behaviors (smoking, poor diet, and reduced physical activity) will increase more in response to dynamic health events in low income and minority communities.

Secondary outcome variable(s)

Given the correlational nature of this research the distinction between primary and secondary outcome variables is not particularly apparent.

Background

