
features with survey data. For example, NHANES survey questions (e.g. Do you now smoke cigarettes?) would be compared with images of cigarette smoking. For Objective 2: We will compare prediction models with and without digital variables. Probability weighted Cox proportional hazard analysis with robust variance estimates will be used to assess the association between each variable from digital media and CHD in univariable and multivariable models. We will use graphical and analytical methods to test the proportional hazards assumption for each analysis. To evaluate the predictive strength of digital data, we will build four predictive machine learning models using a stepwise sequence to select the most parsimonious model using combinations of risk factors. (1. Framingham predictors / American College of Cardiology ASCVD Risk Estimator Plus alone, 2. Framingham predictors / American College of Cardiology ASCVD Risk Estimator Plus + SES, 3. Framingham predictors / American College of Cardiology ASCVD Risk Estimator Plus + digital topics/features, 4. Framingham predictors / American College of Cardiology ASCVD Risk Estimator Plus + digital topics/features+ SES) For Objective 3: We will use Super Learner, the ensemble machine learning approach which allows for the specification of multiple plausible candidate prediction models. Each of the candidate models is applied to a training set and outcomes are predicted using the validation set. A loss function is calculated within each validation set and then averaged across validation sets, which provides the estimated cross-validated risk score for each method. Calibration will be assessed using a calibration plot comparing the predicted probabilities (obtained using fixed regression coefficients of the prediction models) with the observed probabilities. The Super Learner algorithm finds the optimal weighted combination across all of the specified methods. Van der Laan et al. proved the asymptotic efficiency of the Super Learner algorithm and demonstrated that the optimal combination performs at least as well as the best estimators from the candidate models. We will implement Super Learner in R (The R Foundation for Statistical Computing). In this approach generalized estimating equation (GEE) and generalized linear mixed effects models will be explored to account for repeated measures per patient over time. One of the challenges of cost analyses is censoring, since cost may be incomplete and available for some patients and not others. As the dependent variable will be cost, we will be attentive to informative censoring and right skewness, potentially using generalized linear models under a gamma distribution and log link. To account for informative censoring we will use inverse probability of censoring weighting. We will also explore the application of our new nested g-computation approach that allows for informative censoring and time-varying covariates to obtain future cost predictions. Additionally, we will generate summary statistics to describe the cohort and survey responses. We will use the model-based approach of latent class analysis (LCA)- to classify individuals into previously unmeasured subgroups. Variables to include in the LCA will include: demographics, years of platform use, posting: volume, quality, retransmission, and engagement. We will use the Bayesian information criterion to assess goodness of model fit, entropy to assess variations between classes, and the parametric bootstrapped likelihood ratio test to assess if a model with k classes has better performance than k-1 classes. We will then use a regression model to compare with measures of health status, social media perceptions, and readiness/activation for each latent class. Models will be adjusted for demographics.

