
summary statistics to describe patient demographics, survey response data, and digital data usage (e.g. frequency of posting, number of social media platforms). Descriptive data will be presented as mean (SD) for continuous variables and frequencies of participants for categorical variables. 5b Extracting topics and features: We will use the Mallet package for implementation of the Latent Dirichlet Allocation (LDA) method for clustering language data of all participants. The LDA probabilistic model assumes that documents (e.g. Facebook status updates) contain a distribution of topics which then contain a distribution of words. Ultimately, words are grouped together by considering the other words they appear with. Descriptive statistics, t-tests (continuous measures) and chi-squared tests (categorical measures) will be used to compare topics and features with survey data. For example, NHANES survey questions (e.g. Do you now smoke cigarettes?) would be compared with images of cigarette smoking. For Objective 2: We will compare prediction models with and without digital variables. Probability weighted Cox proportional hazard analysis with robust variance estimates will be used to assess the association between each variable from digital media and CHD in univariable and multivariable models. We will use graphical and analytical methods to test the proportional hazards assumption for each analysis. To evaluate the predictive strength of digital data, we will build four predictive machine learning models using a stepwise sequence to select the most parsimonious model using combinations of risk factors. (1. Framingham predictors / American College of Cardiology ASCVD Risk Estimator Plus alone, 2. Framingham predictors / American College of Cardiology ASCVD Risk Estimator Plus + SES, 3. Framingham predictors / American College of Cardiology ASCVD Risk Estimator Plus + digital topics/ features, 4. Framingham predictors / American College of Cardiology ASCVD Risk Estimator Plus + digital topics/features+ SES) For Objective 3: We will use Super Learner, the ensemble machine learning approach which allows for the specification of multiple plausible candidate prediction models. Each of the candidate models is applied to a training set and outcomes are predicted using the validation set. A loss function is calculated within each validation set and then averaged across validation sets, which provides the estimated cross-validated risk score for each method. Calibration will be assessed using a calibration plot comparing the predicted probabilities (obtained using fixed regression coefficients of the prediction models) with the observed probabilities. The Super Learner algorithm finds the optimal weighted combination across all of the specified methods. Van der Laan et al. proved the asymptotic efficiency of the Super Learner algorithm and demonstrated that the optimal combination performs at least as well as the best estimators from the candidate models. We will implement Super Learner in R (The R Foundation for Statistical Computing). In this approach generalized estimating equation (GEE) and generalized linear mixed effects models will be explored to account for repeated measures per patient over time. One of the challenges of cost analyses is censoring, since cost may be incomplete and available for

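### Objective 2's stepwise, most-parsimonious rule leaves the conventional risk factors unprotected in the comparator and does not aim at the AUC increment that H2 is about

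*SAP*

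**What the plan says.** The aim is set in the Protocol under Overall objectives: "Quantify and validate the incremental benefit of adding variables from patients' digital data to conventionally-derived predictive models of CHD". H2, under Primary outcome variable(s), names the measure: "Adding digital data variables to conventionally-derived predictive models will improve the AUC".

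The method is in the SAP, Final Analysis Plan, For Objective 2. It opens with a comparison: "We will compare prediction models with and without digital variables". It then states the model-building rule: "we will build four predictive machine learning models using a stepwise sequence to select the most parsimonious model using combinations of risk factors". The four models are the conventional predictors alone, plus SES, plus digital features, and plus both. The first is printed as "1. Framingham predictors / American College of Cardiology ASCVD Risk Estimator Plus alone". The Protocol's Analysis Plan carries the same rule: "using a stepwise sequence to select the most parsimonious model using combinations of risk factors".

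For Objective 2 neither document gives an entry, removal or parsimony criterion, or says that the conventional predictors stay in. Neither names a primary contrast, an estimator of the AUC difference or an interval. AUC does not appear in the Objective 2 analysis text. Training and validation sets and calibration are described only under Objective 3.

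**The concern.** An increment is only as meaningful as the model it is measured against. H2 needs an intact conventional model and an estimated difference in AUC. The stated rule secures neither.

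- **Stepwise as variable selection.** A genuine risk factor with a modest effect can miss the threshold in about 1000 people and be removed. Model 1 is then a reduced, sample-dependent version of the conventional score. In model 3, a digital feature that merely tracks a conventional factor can take its place. This is plausible here, because the SAP deliberately looks for language tied to known CHD predictors.
- **Stepwise as choice among the four models.** The end product is one preferred model. The size of the digital contribution, which is what the objective asks for, is not the output of that step.

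At stake is whether a reported gain can be read as information beyond established risk factors. Because the rule admits more than one reading, the choice between them could also be made after the data are seen.

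**Working it through.** The plan states no criterion, event count or target AUC difference for Objective 2, so there is no figure to reproduce. The only planned input is N = 1000 (Protocol, Study duration). Everything else below is assumed and shows direction and rough size only.

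**1. Can a genuine predictor be dropped at N = 1000?** For one standardised predictor, the standard error of the log odds ratio is about 1/√(N·p·(1−p)), where p is the outcome share. The expected z is |ln OR|/SE. The chance of removal at two-sided 0.05 is about Φ(1.96 − z).

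| Outcome share | SE | OR 1.15: z, chance dropped | OR 0.82: z, chance dropped |
|---|---|---|---|
| 50% | 1/√250 = 0.063 | 2.21, 40% | 3.14, 12% |
| 30% | 1/√210 = 0.069 | 2.03, 47% | 2.88, 18% |
| 10% | 1/√90 = 0.105 | 1.33, 74% | 1.88, 53% |

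A BIC rule is stricter. It removes a term when z² < ln(1000) = 6.91, that is, when |z| < 2.63.

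**2. First simulation.** Eight independent established predictors (log OR per SD 0.15 to 0.6); 20 digital features, each correlated 0.4 with one of them; backward elimination at p<0.05 in models 1 and 3 alike; 100 replicates; a test set of 10,000. Comparator loss is the test AUC of model 1 with all predictors kept minus its test AUC after elimination. With no direct digital effect (true increment under 0.001):

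| Outcome share | At least one predictor dropped | Mean dropped of 8 | Comparator loss | Gain in same data: stepwise / kept | Gain in new data: stepwise / kept |
|---|---|---|---|---|---|
| about 10% | 94% | 2.1 | 0.7485 − 0.7379 = 0.0106 | 0.0086 / 0.0073 | −0.0095 / −0.0067 |
| about 30% | 64% | 0.8 | 0.7287 − 0.7257 = 0.0030 | 0.0042 / 0.0037 | −0.0047 / −0.0037 |
| about 50% | 55% | 0.7 | 0.7347 − 0.7325 = 0.0022 | 0.0036 / 0.0033 | −0.0034 / −0.0031 |

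Here "kept" means that all conventional predictors are forced into both models. With a true increment of 0.016 to 0.017, a predictor was dropped in 97%, 71% and 63% of replicates. The gain in new data was then 0.0030, 0.0120 and 0.0089 stepwise, against 0.0041, 0.0129 and 0.0090 with the predictors kept.

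**3. Second simulation.** Eight predictors with odds ratios of 1.15 to 1.7 and one protective at 0.82; digital features that are pure proxies.

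- At least one genuine predictor was dropped in 72% to 100% of samples.
- The comparator lost 0.003 to 0.015 AUC at p<0.05, and 0.008 to 0.032 under BIC.
- At 30% cases, p<0.05 and proxy correlation 0.7, a proxy feature was selected in 58% of samples, against 34% with the conventional predictors kept.
- With one rule applied to models 1 and 3, the mean gain from pure proxies in new data was negative in every setting.

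**4. Sensitivity to effect size.** With a somewhat stronger set of assumed effects, at 50% and 30% cases and p<0.05, the drop rate fell to 16% to 34% and the loss to 0.001 to 0.002.

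**The case against.** The strongest defence is that the wording need not mean deletion. The conventional set appears in all four listed models, so the sequence could mean adding blocks to an intact core. On that reading nothing leaves model 1. The defence stands as a possible reading, but the text does not commit to it, and the stated goal would still be selection of one compact model.

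A reader might infer several stronger points that the documents do not support.

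- **That the plan picks a winner and never estimates the increment.** Objective 2 opens with the comparison H2 needs, and the listed models contain the contrasts 3 versus 1 and 4 versus 2. The increment is intended; its estimation is not specified.
- **That parsimony favours the smallest model by construction.** Parsimony rules trade fit against size, so this does not follow.
- **That H2 could be supported in independent data without new information.** With one rule for all models, pure proxies gave negative gains in new data. Positive gains appeared only when the comparator was reduced but the digital features were entered unselected, under BIC with proxy correlation 0.7. The SAP names BIC only for the latent class analysis.
- **That the slash between the two scores lets the weaker one serve.** The objectives give them as examples. The choice is open, and no intent can be read from it.

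It is also fair that most of the optimism in the first simulation comes from selecting and evaluating features on the same data. That is a separate problem. The comparator loss was measured in new data, so validation alone would not remove it.

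**Conclusion.** The point holds as a mismatch between rule and aim that should be corrected. The plan names a selection method that does not protect the conventional predictors and has a goal other than the AUC increment. Read as variable selection, it would often remove at least one genuine predictor at N = 1000. It would cost the comparator roughly 0.003 to 0.015 AUC at p<0.05 and up to about 0.03 under a BIC-type criterion, and it would admit uninformative proxies more often. The loss can be as small as 0.001 to 0.002 if the predictors are strong and cases are plentiful.

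These sizes rest on assumed odds ratios, independent predictors, a logistic outcome and outcome shares of 10% to 50%; none of them is in the documents. The net effect on the estimated gain has no fixed direction. Same-data gains were slightly larger under stepwise selection, while new-data gains were slightly smaller. The case for change is therefore that the contrast becomes hard to interpret, not that a false positive has been shown.

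**What to change.** In the SAP (Final Analysis Plan, For Objective 2) and the Protocol's Analysis Plan:

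1. Delete the stepwise and most-parsimonious rule.
2. Prespecify one conventional score, or report the result for both. Keep all its predictors in all four models without selection.
3. Confine selection or penalisation to the digital features, and carry it out inside resampling so that the reported AUCs are corrected for optimism.
4. Report the AUC difference with a confidence interval for model 3 minus model 1, which is H2 as worded, and for model 4 minus model 2 as its SES-adjusted companion.

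The cost is wording and a little extra analysis, with no new data. The apparent digital gain may look slightly smaller: in the first simulation with a true increment, the same-data gain fell from 0.0198 to 0.0184 at an outcome share of about 10%. The final model will also be less compact.

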
some patients and not others. As the dependent variable will be cost, we will be attentive to informative censoring and right skewness, potentially using generalized linear models under a gamma distribution and log link. To account for informative censoring we will use inverse probability of censoring weighting. We will also explore the application of our new nested g-computation approach that allows for informative censoring and time- varying covariates to obtain future cost predictions. Additionally, we will generate summary statistics to describe the cohort and survey responses. We will use the model-based approach of latent class analysis (LCA)- to classify individuals into previously unmeasured subgroups. Variables to include in the LCA will include: demographics, years of platform use, posting: volume, quality, retransmission, and engagement. We will use the Bayesian information criterion to assess goodness of model fit, entropy to assess variations between classes, and the parametric bootstrapped likelihood ratio test to assess if a model with  $k$  classes has better performance than  $k-1$  classes. We will then use a regression model to compare with measures of health status, social media perceptions, and readiness/activation for each latent class. Models will be adjusted for demographics.

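### Objective 3 checks calibration of probabilities although its outcome is cost, and H3 claims better prediction with no comparator, loss or contrast named

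*SAP*

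**What the plan says.** The protocol (Primary outcome variable(s)) fixes the outcome: "The third objective outcome measure will be health care utilization measured by cost". The SAP (Final Analysis Plan, Objective 3) agrees: "As the dependent variable will be cost, we will be attentive to informative censoring". It adds that a gamma model with log link may be used and that censoring will be handled by inverse probability weighting.

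Within the same Objective 3 text the SAP states: "Calibration will be assessed using a calibration plot comparing the predicted probabilities". The protocol's Analysis Plan has the same sentence, with the check described as "comparing the predicted probabilities (obtained using fixed regression coefficients of the prediction models) with the observed probabilities".

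H3 (protocol, Primary outcome variable(s)) says that digital variables identified for patients with and without heart disease "will better predict future health care utilization costs for the health system". H2, in the same section, is worded differently: "Adding digital data variables to conventionally-derived predictive models will improve the AUC".

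Under Overall objectives, Objective 2 is to "Quantify and validate the incremental benefit of adding variables" from digital data to conventional models. Objective 3 is to "develop and evaluate models that use digital media data to predict health care utilization", with cost given as an example.

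The Objective 3 method is Super Learner. A loss is averaged over validation sets for each candidate method, and the candidates are then combined with optimal weights. The loss is not named.

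**The concern.** There are two gaps in the same objective.

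- **Calibration.** A model for mean cost yields an amount, not a probability. A plot of predicted against observed probabilities therefore has nothing to display unless cost is first made binary, and no threshold or two-part model is defined. At stake is whether predicted costs match observed costs, which matters for a model meant to forecast costs for a health system.
- **Comparator.** 'Better' needs a referent. H2 supplies a reference (conventional models) and a metric (AUC); H3 supplies neither. If the plan is followed, the report will contain a cross-validated loss for each candidate method, with no comparison that could support or refute H3.

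**Working it through.** The documents give no sample-size, power or accuracy figure for Objective 3, so there is nothing to reproduce. The check is a reading of the text, followed by two illustrations on assumed values.

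**1. Outcome against check.** The outcome is cost (protocol, Primary outcome variable(s); SAP, Objective 3). The model suggested for it, a gamma model with log link, predicts mean cost. The check concerns probabilities obtained from fixed regression coefficients. A weighted combination of candidate algorithms in general has no single set of coefficients either. Both features of the sentence would suit an event model such as those in Objective 2, but the documents do not say it was meant for them. The analysis plan has one calibration sentence, under Objective 3, and none in the Objective 2 text. On either reading, one of the two objectives has no usable calibration check.

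**2. H2 against H3.**
- Objective 2: reference stated, AUC stated, four predictor sets listed, two of them without digital variables.
- Objective 3: no reference, no named loss, no predictor sets, no contrast. Super Learner compares algorithms with one another and with their combination. That does not compare predictors with and without digital data.

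**3. Can a cross-validated loss reveal miscalibration?** Assume squared-error loss. Let r be the R² of the predictions after recalibration and b the calibration slope. With outcome variance scaled to 1, the predictions have variance r/b² and covariance r/b with the outcome. The squared error is then 1 − 2r/b + r/b², so

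R² of the uncorrected predictions = r(2b − 1)/b², and their spread is too wide by 1/b − 1.

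- r = 0.10, b = 0.9: 0.10 × 0.8/0.81 = 0.099 (spread 11% too wide)
- r = 0.10, b = 0.8: 0.10 × 0.6/0.64 = 0.094 (25% too wide)
- r = 0.10, b = 0.7: 0.10 × 0.4/0.49 = 0.082 (43% too wide)
- r = 0.05, b = 0.8: 0.05 × 0.6/0.64 = 0.047
- r = 0.20, b = 0.8: 0.20 × 0.6/0.64 = 0.188

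Predictions spread 25% too wide change R² by about 6% of its value (0.006 of 0.10).

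**4. Can a loss for a model with digital data show what those data add?** Assume a reference score with R² = 0.10, and a digital feature with no effect of its own but correlation ρ with that score. The digital feature alone then has R² = 0.10 × ρ²:

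- ρ = 0.5: 0.10 × 0.25 = 0.025
- ρ = 0.7: 0.10 × 0.49 = 0.049
- ρ = 0.9: 0.10 × 0.81 = 0.081

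The combined model has R² = 0.10, so the true gain is 0 in every row.

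**5. Precision of a grouped cost plot.** The target is 1000 participants (protocol, Study duration). The relative standard error of a group mean is CV/√n. For an assumed coefficient of variation of 2 to 4, before censoring weights:

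- deciles (n = 100): 2/10 to 4/10, or 20% to 40%
- quintiles (n = 200): 2/14.1 to 4/14.1, or 14% to 28%

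Deciles would be noisy, so the fix uses coarser groups or a smoothed curve, with intervals.

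**The case against.** The calibration sentence may be a slip: reading predicted values for predicted probabilities makes it workable, and Overall objectives gives cost only as an example of utilization. The repair is indeed short. But the outcome section and the SAP both settle on cost, and the reader would still have to guess which objective the plot serves, on what scale, and how censored costs enter.

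A reader might infer that the plan offers no measure at all of what digital data contribute. The documents do not support that. The general analysis text, ahead of the objective-specific sections, promises random-forest measures of each feature's contribution, and nothing excludes a candidate model without digital variables. Neither is a with/without comparison, however, and neither is tied to H3.

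A reader might also take H3 to be incremental, like H2. That is uncertain. The incremental claim is made for Objective 2 only. H3 could mean simply that digital data predict cost, or that variables identified separately for patients with and without heart disease predict better than undifferentiated ones.

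Nor do the documents say that the comparator and loss will be chosen after the data are seen; they are silent on timing. Finally, the protocol calls the research correlational and draws no firm line between primary and secondary outcomes. This limits the weight of the point, but H3 is still a directional hypothesis.

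**Conclusion.** Both parts hold. The calibration check is wrong as written for a cost outcome; this rests on the text alone and is firm. The missing comparator, loss and contrast are also plain from the text. What H3 was meant to compare is open, so confidence in any one remedy for that part is moderate.

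The R² figures are not forecasts for this study. Every R², slope and correlation is assumed, and the algebra is for squared error, while the plan names no loss and suggests a gamma model. They show only that such a loss need not reveal miscalibration or added value.

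This is a specification gap that should be closed before the Objective 3 analysis. It does not undermine the study's data collection or its other objectives.

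**What to change.** **Calibration.** State which objective the probability plot serves. For Objective 3, replace it with a plot of censoring-weighted mean observed cost against mean predicted cost, on the untransformed cost scale, by groups of out-of-fold prediction (for example quintiles, or a smoothed curve), with confidence intervals. Add a calibration intercept and slope, and state their scale.

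**H3.** State what 'better' is compared with, and name one loss in advance.
- *If incremental:* fit the same Super Learner library with and without digital features on top of a reference set the study already plans to collect: demographics, income and education (survey), insurance type (authorization), and cardiovascular disease status (diagnosis codes, or self-report for outside patients). Use the same patient-level folds, censoring weights and handling of missing items in both fits. The last matters because the consent process lets participants skip questions, so the reference set will not be complete for everyone. Place both fits inside an outer cross-validation layer, and report the paired difference in the named loss with a patient-level confidence interval.
- *If H3 concerns variables identified separately for patients with and without heart disease:* make separate against undifferentiated variables the paired contrast, evaluated in the same way.
- *If no comparison is meant:* drop 'better' from H3.

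**Cost.** SAP wording and extra computing. A confidence interval for the difference between two ensembles needs nested cross-validation of both fits, which is more than one additional run. No new data or participants are needed.
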